3.2.1.1 Erythema & Edema Visual Assessment Method

Score	Description of Response
0	No visible response
1	Mild Response. Diffused, patchy, not well-defined, just barely perceived erythema . No perceivable edema.
2	Moderate Response. Perceivable erythema is obvious, with diffused redness. Pink or red in color, area well defined . No edema.
3	Severe Response. Obvious erythema. Definite red in color, area well defined . Edema Present.
4	Extreme Response. Bright, fiery red erythema . Edema is present.

3.2.1.2 Skin stripping (Denudation) Scale

Score	3M Denudation Severity Scale
0	No sign of denudation.
1	Trace amount of denudations in epidermis. (Slight glazed appearance) .
2	Partial thickness denudations (first sign of pitting in the skin) extending up to the glistening layer of the epidermis. (Moist and/or wet surface) .
3	Full thickness denudations extending into the dermis. (Exudates present on the test site)
4	Full thickness denudations extending into the dermis or in combination with an extreme Erythema/Edema response.

Erythema with edema will be assessed at T0 and T24. Skin stripping will be assessed at T24.

7.2.5 Photography

Photographs will be taken at T24 to document skin reactions. The photographs may be used in publications to visually document the erythema scores determined by the Expert Skin Grader.

8.0 Assessment of Safety

8.1 Safety Parameters

The principle measure of safety will be the incidence of tape-related adverse events reported during the study.

8.2 Anticipated Events

For the purpose of this study, any signs or symptoms of expected events associated with the tape application/removal including erythema, skin stripping, itching and discomfort upon removal may or may not be coded as an adverse event based on the investigator assessment.

If any of these irritation parameters appear to be highly exacerbated, more than normally associated with use conditions in this type of population, the event will be recorded as an adverse event. This can only be determined by the investigator.

8.3 Adverse Events

The Investigator is responsible for identifying adverse events that occur to each subject throughout the study and follow-up period. An adverse event can occur at any time during the conduct of the study, in any phase of the study or after the study is completed. An adverse event can be identified by the Investigator or reported by the subject.

For this study, any non-device adverse events (e.g. common cold, falls, systemic illnesses, etc.) will not be recorded. All device-related and serious adverse events will need to be reported to the sponsor.

Note: The Federal Privacy Rule (HIPAA) specifically permits the use and disclosure of protected health information “without written authorization of the individual” when used for public health activities such as reporting adverse events, tracking FDA-related products, enabling recalls, repairs, replacements, lookbacks, or conducting post-market surveillance [45 CFR 164.512]. This use and disclosure is subject to the minimum necessary standard, i.e. “the minimum necessary to accomplish the intended use, disclosure, or request” [45 CFR 164.502(b)(1)].

Definitions:

- Adverse event (AE) means any undesirable clinical occurrence in a subject whether or not it is considered to be device related.
- Device-related adverse event (i.e. adverse device effect) is an AE considered by the Investigator to have a reasonable likelihood of being associated with the investigational device.
- Serious adverse device effect is a device effect that has a serious adverse effect on health or safety causing hospitalization or prolonged hospitalization, or is life threatening or causes death.
- Unanticipated adverse device effect is any serious adverse device effect on health or safety or any life-threatening problem or death caused by, or associated with a device if that effect, problem or death was not previously identified in nature, severity or degree of incidence in the investigational plan or application, or any other unanticipated serious problem associated with a device that relates to rights, safety and welfare of subjects.

Recording and Reporting

The Investigator records each material-related adverse event on an Adverse Event CRF. Documentation includes the description, severity, seriousness, date of onset and resolution, relationship to the investigational material, action taken and outcome.

The Investigator must promptly report an adverse device effect to the 3M study monitor. If the adverse device effect is also considered by the Investigator to be serious and/or unanticipated, the Investigator must report it to the IRB as soon as possible and within IRB requirements.

A serious AE involving a non-3M commercialized product is reported to the 3M study monitor and IRB.

If a subject has no adverse device effect during the study, the absence of such must be recorded on the CRF.

9.0 Statistics

9.1 Data Sets Analyzed

Data obtained for all subjects that enter the study and have samples applied will be analyzed in this study.

9.2 Statistical Methods

9.2.1 Efficacy Analyses

The BCA results will be summarized, and log-transformed data will be compared to a previous study.

Cumulative FLACC scores will be calculated from this study and compared to a previous study.

Summary statistics will be provided for all variables tested in the study. This includes tables with mean, median, std dev, min, and max, as well as frequency distribution tables when needed.

9.2.2 Safety Analyses

The analyses listed above for erythema, denudation, and discomfort will be carried out as the safety analyses.

9.3 Sample Size Justification

The sample size of 20 is needed so that the one-sided Wilcoxon signed rank test will have approximately 80% power to detect a $p > 0.5$ assuming that the observed $p = 0.85$ with significance level set at 0.05, where $p =$ probability of observing a higher ordinal FLACC score in one sample than the other sample when comparing to a previous study.

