9.4 Procedures for Accounting for Missing, Unused, and Spurious Data

Subjects who do not comply with the requirements of this study will be dropped. Any subject who withdraws from this study or is dropped for cause may be replaced to ensure that a minimum of 20 subjects complete the study. In the event that lost subjects have a material effect on the analysis of the study and the importance of the conclusions drawn from the study, efforts will be made to consult with the study requester and a statistician to discuss how to best address the issues.

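### Section 9.3's inputs do not lead to about 80% power with 20 children: most one-sided calculations give more, and its definition of p does not fix the power

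*Combined protocol and SAP*

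**What the plan says.** Section 9.3 (Sample Size Justification) names a "one-sided Wilcoxon signed rank test" and sets the other inputs: 20 subjects, p = 0.85 against a null value of 0.5, "with significance level set at 0.05", and a resulting power of roughly 80%. Its wording is: "The sample size of 20 is needed so that the one-sided Wilcoxon signed rank test will have approximately 80% power". It describes p as the "probability of observing a higher ordinal FLACC score in one sample than the other sample", in a comparison with a previous study.

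Section 9.4 says that subjects who withdraw or are dropped "may be replaced to ensure that a minimum of 20 subjects complete the study". Section 2.6 allows up to 24 to be enrolled to reach 20. So 20 is a target for completers, and no dropout allowance is stated within it. Section 9.3 gives no formula, software, rule for ties or zero differences, or size of the previous study.

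**The concern.** A sample size statement should return its own output when its inputs are put into the test it names. This one does not under the usual formula, and the departure is larger than rounding or the word 'approximately' would cover.

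Section 9.3 is the only justification for applying tape to 20 healthy children aged 6 months to 4 years, who, according to section 2.3, gain nothing medically from taking part. An ethics committee or statistician cannot check the figure as written, and the claim that 20 children are required for 80% power is not supported by the calculation described. Whether a signed-rank test suits a comparison with a previous study is a separate question. Here the named test is taken as given.

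**Working it through.** **Inputs (all from section 9.3).** N = 20; Wilcoxon signed rank; one-sided; alpha 0.05; p = 0.85 against 0.5; stated power about 80%. Write D for a difference, and D1 and D2 for two independent differences.

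**1. Attempt to reproduce the stated figure: closed form.** Noether's formula for the signed-rank test uses p = P(D1 + D2 > 0).

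- N for 80% = (1.645 + 0.842)² / [3 × (0.85 − 0.5)²] = 6.18 / 0.3675 = 16.8, so 17.
- Power at 20 = Φ(√60 × 0.35 − 1.645) = Φ(2.711 − 1.645) = 85.7%.
- Power at 17 = 80.4%; at 16 = 78.2%.
- Value of p giving 80% power at 20 = 0.5 + 2.486/√60 = 0.82.

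Using the finite-sample variance instead: null mean 20 × 21/4 = 105, SD √(20 × 21 × 41/24) = 26.8, expected rank sum 210 × 0.85 = 178.5. Power = Φ(73.5/26.8 − 1.645) = 86.4%, or 86.0% with a continuity correction. The stated 80% is not reproduced.

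**2. Same p, exact critical value.** At N = 20 the test rejects when the negative rank sum is 60 or less (actual alpha 0.0487). Simulating a normal shift with P(D1 + D2 > 0) = 0.85 gives 92.3% at 20, about 80% at 14 and 83% at 15. Logistic, Laplace and uniform shifts also give about 92% at 20.

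**3. The section's own wording of p.** If p is the chance of a positive difference, P(D > 0) = 0.85, the signed-rank power depends on the sizes of the differences as well as their signs:

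- normal shift: 99.6% (Laplace shift: 98.2%);
- sign independent of size: 92.2%;
- extreme case, all negative differences the largest in size: three negatives give a rank sum of 20 + 19 + 18 = 57, which still rejects; four give 57 + 17 = 74, which does not. Power = P(Bin(20, 0.15) ≤ 3) = 64.8%.

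The exact sign test rejects at 15 or more positives (actual alpha 0.0207) and has power 93.3%.

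**4. What comes near 80%.** Two-sided closed form: Φ(2.711 − 1.960) = 77.4% at 20 (78.3% with the finite-sample variance). N for 80% = (1.960 + 0.842)²/0.3675 = 21.4, so 22.

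| Calculation, p = 0.85 | Power at 20 | N for 80% |
|---|---|---|
| Stated in section 9.3 (one-sided) | about 80% | 20 |
| Closed form, one-sided, P(D1 + D2 > 0) | 85.7% | 17 |
| Exact critical value, one-sided, normal shift, same p | about 92% | about 14 |
| Signed rank, one-sided, P(D > 0), sign independent of size | about 92% | about 14 |
| Signed rank, one-sided, P(D > 0), normal shift | over 99% | at most 10 (89% at 10) |
| Signed rank, one-sided, P(D > 0), extreme case | about 65% | not computed |
| Closed form, two-sided | 77.4% | 22 |

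**The case against.** The strongest reply is that 85.7% and 17 are not the true figures for this test. They come from an approximation, and they use P(D1 + D2 > 0), whereas section 9.3 words p as the chance of a higher score. On that wording power can lie anywhere from about 65% to over 99%, and the stated 80% falls inside that span. This stands. It rules out saying that the power is 86%, or that three children too many are enrolled. It does not rescue the statement: an output that the inputs leave undetermined cannot be said to follow from them, and values below 80% need an unusual pattern in which the negative differences are among the largest.

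Three stronger readings are tempting, and the documents do not support them.

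- *The study becomes underpowered once a few differences are zero.* The usual signed-rank test discards zeros, and FLACC is ordinal, so some zeros are plausible. With 15 non-zero differences the closed form drops to Φ(√45 × 0.35 − 1.645) = 75.9%. But with p = 0.85 among those 15, the exact-critical-value simulation (normal shift, P(D1 + D2 > 0)) still gives 83% and the exact sign test 82%, so the shortfall comes from the approximation. The documents give no zero rate. Filming a relaxed child (sections 6.1.4 and 7.1.2) bears on that child's baseline score, while p in section 9.3 concerns a comparison with a previous study.
- *A two-sided calculation was mislabelled as one-sided.* This is possible, but so is a target of 85% power, for which the one-sided closed form gives 19.6, so 20. The documents settle neither.
- *A dropout allowance explains 20.* 17/(1 − 0.15) = 20, but no 15% rate is stated, and section 9.4 makes 20 a completer minimum.

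A rank-sum comparison of 20 children with 5 previous subjects would give 78%. That is a different test, and the 5 is an assumption; with 10 previous subjects it gives 93%.

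**Conclusion.** The point holds as a reporting error. The stated power of about 80% and the claim that 20 children are required do not follow from section 9.3's one-sided inputs. With p read as P(D1 + D2 > 0), power at 20 is 85.7% by the closed form (17 needed) and about 92% with exact critical values under a normal shift (about 14 needed). With p read as the section words it, power is not fixed by p alone. Apart from the constructed worst case, the one-sided signed-rank calculations run on that wording give 92% or more.

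The discrepancy is mostly conservative, and nothing here calls for more children. The result rests on taking the signed-rank test as named, on 20 usable non-zero differences, and, for the simulated figures, on the assumed shapes stated above.

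**What to change.** Keep N = 20 and rewrite section 9.3.

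1. Name the formula or software, the sidedness, and which p is meant: P(D1 + D2 > 0) or P(D > 0).
2. Give the power that matches. For example: *With 20 children and a one-sided 0.05 signed-rank test, power is about 86% at p = 0.85 by the Noether formula, where p = P(D1 + D2 > 0); 80% power is reached at p = 0.82.* If the calculation was two-sided, say so and give 77%. If exact critical values are used, report that figure with its assumed distribution.
3. Remove the statement that 20 children are needed for 80% power.
4. State the size of the previous study and how its scores are paired with these, since the meaning of p depends on it.
5. If sensitivity to zero differences is shown, define p among the non-zero differences and use that same p throughout. A p that counts ties as one half should not be combined with it: with 40% zeros such a p cannot exceed 0.60 + 0.20 = 0.80, so 0.85 is impossible. With 25% zeros, 0.85 means (0.85 − 0.125)/0.75 = 0.967 among the non-zero differences, and the closed form then gives about 93%, not 75.9%.

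The cost is one reworded paragraph and retrieval of the original calculation. Enrolment, procedures and the 20-completer target do not change.

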2.4 Investigational Material Application

The product to be tested is an investigational adhesive tape for medical use and will be used as intended. There will be no control tape for this study. Tape will be provided in 1-inch wide widths and will be applied as 1-inch by 1.5-inch strips onto the back of the subject. The tape will be allowed to remain in place for approximately 24 hours before removal. The tape will be applied and removed according to the procedures listed in Appendix 1.

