3.0 Study Objectives and Purpose

The objective of this study is to determine the relative [REDACTED]. A three-prong multidimensional evaluation consisting of expert grader, subject discomfort assessment, and laboratory assessments will be used. One pre-study visit will take place up to 7 days prior to the start of the study. The study will be conducted over two days with one tape sample applied and removed. Assessments will be taken on the final day. This is to mimic a normal tape application in health care practice. Assessments will be compared to those taken in a previous study.

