4.2 Primary and Secondary Endpoints

The primary endpoint will be the change in the subject discomfort (from baseline to the final assessment) using the FLACC (face, legs, activity, cry, consolability) scale.

Secondary endpoints will be laboratory assessments (hair and skin cell quantification), skin erythema (as made by an expert skin grader), skin denudation (skin stripping), and sample lift.

These endpoints will be compared to those taken in a previous study.

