4.3 Randomization and Blinding

There will be no randomization used in this study, as only 1 test sample will be evaluated.

The discomfort assessor will be observing the video recording of the subject's full anterior side.

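### Section 9.3 justifies N=20 with a signed rank test, but the FLACC comparison it describes is between two studies with no stated pairing, and the quoted power does not follow from its inputs

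*Combined protocol and SAP*

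**What the plan says.** Section 9.3 is the only place where a hypothesis test is named: "The sample size of 20 is needed so that the one-sided Wilcoxon signed rank test will have approximately 80% power to detect a" value of p above 0.5. The assumed p is 0.85 and the significance level is 0.05. The section defines p as the "probability of observing a higher ordinal FLACC score in one sample than the other sample when comparing to a previous study".

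The other sections also describe a comparison with an external study:
- Section 3.0: "Assessments will be compared to those taken in a previous study".
- Section 4.2: "The primary endpoint will be the change in the subject discomfort (from baseline to the final assessment) using the FLACC" scale, and then "These endpoints will be compared to those taken in a previous study".
- Section 9.2.1: "Cumulative FLACC scores will be calculated from this study and compared to a previous study". No test is given.

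On design, Section 2.4 states "There will be no control tape for this study", and Section 4.3 states "There will be no randomization used in this study, as only 1 test sample will be evaluated". Section 9.5 asks that departures from the statistical plan be explained in the final report.

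**The concern.** A signed rank test works on differences within pairs, or on differences from a constant. Section 9.3 defines its effect across two samples from two studies, and the available text supplies neither pairs nor a constant. Because Section 9.2.1 names no other test, the primary comparison has no fitting pre-specified method. The analyst would have to choose one, and nothing in the plan requires that choice to be made before the data are seen. Section 9.5 would bring the choice into the report, but disclosure is not pre-specification.

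Two further gaps follow. The plan calls the test one-sided but does not say whether higher or lower FLACC in this study is the alternative. And the sample size rests on a test that cannot be applied to the comparison as described.

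**Working it through.** **Inputs from Section 9.3:** n = 20, one-sided α = 0.05 (z = 1.645), power about 80% (z = 0.842), p = 0.85 against 0.5. **Not in the documents:** the size m of the previous study and the distribution of its scores. Values of m below are assumptions.

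**1. The plan's own figure.** Noether's signed rank formula:

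n = (1.645 + 0.842)² / [3 (p − 0.5)²] = 6.18 / (3 × 0.1225) = 16.8, so 17 children.

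Power at n = 20: Φ(√(3 × 20) × 0.35 − 1.645) = Φ(2.711 − 1.645) = Φ(1.066) = 85.7%.

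Neither matches 20 children for about 80%. A two-sided test comes closer (21.4, so 22 children; 77.4% power at 20), but Section 9.3 says one-sided. In this formula p is the chance that the sum of two independent paired differences is positive, which is not the p that Section 9.3 defines. Simulation with normal differences at n = 20 gives about 92% power under the formula's meaning of p, and over 99% if p is the chance that a single difference is positive. Every one-sided reading tried therefore exceeds 80%.

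**2. Is there anything to pair?** Three sources of pairing are conceivable:
- Two tapes on one child: excluded, since there is one test sample and no control (Sections 2.4 and 4.3).
- A child here matched with, or the same as, a child in the earlier study: not described. Section 2.6 describes enrolling up to 24 subjects and mentions no link to earlier ones.
- Baseline and removal in the same child (Sections 4.2 and 7.1.2): a genuine pair, but it asks whether removal causes discomfort, not how the two studies differ.

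**3. Which FLACC variable?** Section 4.2 uses change from baseline, Section 9.2.1 a cumulative score, and Section 9.3 an ordinal score. Nothing says these are the same quantity.

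**4. Power for a test that fits.** The p in Section 9.3 is the parameter of the two-sample rank-sum test. Noether's formula, with 20 children here and m in the previous study:

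Power = Φ(√[12 × 20m/(20 + m) × (p − 0.5)²] − 1.645)

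At p = 0.85:
- m = 5: Φ(√5.88 − 1.645) = 78.2%
- m = 6: Φ(√6.785 − 1.645) = 83.1%
- m = 10: Φ(√9.8 − 1.645) = 93.1%
- m = 20: Φ(√14.7 − 1.645) = 98.6%

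At p = 0.70 with 20 versus 20: Φ(√(12 × 10 × 0.04) − 1.645) = Φ(2.191 − 1.645) = about 71%.

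The formula ignores ties. Simulation with tied 0–10 scores at p = 0.85 (ties counted one half) gave 86–89% (m=5), 90–93% (m=6), 97–98% (m=10) and over 99% (m=20). Those runs used scores from 0 to 10. A change score can run from −10 to +10 and was not simulated.

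**The case against.** **The within-child reading.** The two samples might be the baseline and removal recordings of one child, with 0.85 taken from the earlier study. The signed rank test would then suit the change endpoint of Section 4.2. The wording is loose enough for this to be raised, but it does not fit a p defined by comparison with a previous study, and it leaves the between-study comparison without a test.

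**A naming slip.** Since p as defined is the rank-sum parameter, the authors may simply have written the wrong test name. That is plausible and would make this a wording error. It would still need correcting, because Section 9.2.1 does not supply the right name.

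**Redaction.** The objective in Section 3.0 is partly blacked out. The point is therefore limited to what the available text describes. The documents never state outright that the studies are unpaired; that is inferred from the design.

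**Two stronger readings that do not stand.**
- A reader might infer that type I error is badly inflated. Treating the earlier study's observed median as a constant would indeed distort it: in simulation with normal scores, the error at nominal 5% was about 18% for m=10 and 7% for m=100, and results for zero-heavy scores ranged far more widely. But the plan does not propose that procedure and the distributions are assumed, so these figures carry no weight here.
- A reader might infer that the study is underpowered. At the plan's p = 0.85 the figures do not show that, unless the previous study had about five children or fewer. Equally, 20 children cannot be called adequate at every effect size, as the 71% at p = 0.70 shows.

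**Conclusion.** The point holds as a mismatch between test and comparison, and it should be fixed before analysis. The only named test does not fit the between-study FLACC comparison that carries the primary endpoint, its direction is unstated, and three sections name three different FLACC variables. The stated power is not reproduced: about 86% by Noether's signed rank formula rather than about 80%, an error on the conservative side. With a rank-sum test at p = 0.85 and one-sided 0.05, 20 children give at least 80% power once the previous study supplies about 6. This rests on Noether's approximation, on assumed values of m, and on p = 0.85 applying to whichever FLACC variable is finally chosen.

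**What to change.** - In Sections 9.2.1 and 9.3, replace the signed rank test with the Wilcoxon rank-sum (Mann-Whitney) test, with mid-ranks for ties, comparing this study with the previous one. State the direction of the one-sided alternative.
- Reconcile the FLACC variable across Sections 4.2, 9.2.1 and 9.3, and define p on it.
- Identify the previous study's n in Section 9.3 and restate power for the rank-sum test at that n, with at least one p below 0.85.
- If child-level scores from the previous study are not available, say in Section 9.2.1 that the between-study comparison is descriptive. Keep the signed rank test only for the within-child change from baseline, with p redefined to match.

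The cost is mainly wording, and no extra children are needed at p = 0.85 if m is about 6 or more. The real demand is for child-level historical FLACC scores; the documents do not show that these are available or were scored in the same way. No choice of test removes non-randomised differences between the two studies, and the report should say so.
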